Testing the Impact of Two Posters on Contraceptive Knowledge, Contraceptive Preferences, and Perceived Pregnancy Risk

NCT number NCT03372369

Document Date December 22, 2017

Primary Investigator [name] PhD

Co-Primary Investigator [name] [name]

Co-Investigators [name]; [name];

[name]; [name]

[name], PhD

Study Design

We survey women before and after random administration of one of two educational posters informing readers about contraception. Baseline data for both groups will be collected on our three outcomes: contraceptive knowledge, willingness to use effective contraception, and perceived pregnancy risk. Participants will then be randomly shown one of the two fact sheets. Then post-exposure questions on the three outcomes will be asked.

Comparators

Shown in Figures 1 and 2 are the two posters that will be tested in this clinical trial.

[figure not shown]
Procedures

We will use Amazon Mechanical Turk to recruit participants.

The survey will first be tested with N=20 participants using the procedures described below. This will be done to estimate the length of time necessary to complete the survey so that accurate time estimates can be provided to potential participants. This will also enable the researchers to ensure that any technical problems with the survey are corrected before the main research data is collected. Data collected in this phase will not be analyzed unless no changes are made to the study materials after reviewing the data.

Once the survey procedures are tested, we will recruit approximately N=1000 participants to complete the survey (final N=990).

Figure 1: CDC Contraceptive Poster

CS 242797

U.S. Department of
Health and Human Services
Centers for Disease
Control and Prevention

CONDOMS SHOULD ALWAYS BE USED TO REDUCE THE RISK OF SEXUALLY TRANSMITTED INFECTIONS.

Other Methods of Contraception

[figure not shown]
Lactational Amenorrhea Method: LAM is a highly effective, temporary method of contraception.

Emergency Contraception: Emergency contraceptive pills or a copper IUD after unprotected

intercourse substantially reduces risk of pregnancy.

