Adapted from World Health Organization (WHO) Department of Reproductive Health and Research, Johns Hopkins Bloomberg School of Public Health/Center for Communication Programs (CCP), Knowledge for health project, Family planning: a global handbook for providers (2011 update), Baltimore, MD; Geneva, Switzerland: CCP and WHO; 2011; and Trussell J. Contraceptive failure in the United States. Contraception 2011;83:397-404.

Figure 2: New Contraceptive Poster

The study uses an online survey. Subjects will be recruited through Amazon Mechanical Turk's website. Amazon Mechanical Turk is an online service, which allows individuals to post surveys to be completed for a small amount of money. The job posting will include a very general description of the study, but no indications about the eligibility criteria. If a person is interested in participating, they will click on a link, which will take them to a short screening Qualtrics survey. If the person is eligible based on the screening survey, they will be given permission to view and complete the full survey. Data from the screening survey will not be downloaded or kept. The full survey will also be posted on Amazon Mechanical Turk, with the same general description of the study methods. If an eligible person is interested in completing the full survey, they will click on the link in the posting, which will take them to the full Qualtrics survey. There they will see the informed consent information and will be required to give their informed consent before they participate in the survey. We expect that the survey will take 30 minutes, on average, to complete.

After completing the survey, the survey will show the participant a unique code that they can enter into the Amazon Mechanical Turk form. This will be used to ensure that study participants are compensated for completing the survey. This code will not be recorded in our data set. Study compensation \$0.05 for the screening survey and \$3.60 for the full survey. This is approximately equivalent to the federal minimum hourly wage, which should be a reasonable but not coercive incentive for participants.

The study was approved by the University of North Carolina at Chapel Hill Institutional Review Board (IRB number 17-2955).

Measures

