This study measured change in the mean scores for three primary outcomes: contraceptive knowledge, effectiveness of most likely contraceptive method used in the next year, and accuracy of perceived pregnancy risk. We gathered baseline and follow-up measures for each of these outcomes immediately before and after the intervention, respectively.

Contraceptive knowledge was measured objectively using the 25-item Contraceptive Knowledge Assessment.¹ This produced a score between 0 (0% correct) and 25 (100% correct). Our contraceptive knowledge outcome was the change in this score between baseline and follow-up.

Effectiveness of most likely contraceptive method was operationalized using a woman's intention to continue using her current contraceptive method and the contraceptive method she reported being most likely to switch to were she to change methods in the next year. This measure was intended to be a realistic measure of the contraceptive method that women were most likely to use in the next year. We first asked women at both baseline and follow-up: "Do you intend to use the same birth control method(s) that you are currently using for the next year?" If the woman said she intended to keep her contraceptive method(s), the effectiveness of the most effective method she used in the past three months was used as her most likely method of contraception. The effectiveness of contraceptive methods was scored using the following WHO-defined categories²: IUDs, implants, and sterilization were considered highly effective (score = 3, 0-1% annual failure rate); the pill, patch, ring, and injection were considered effective (2, 2-9% annual failure rate); condoms, withdrawal, fertility tracking, and other methods were considered less effective (1, 10-30% annual failure rate); and no method

was its own category (0, 85% annual failure rate). If a woman said she did not intend to keep her current contraceptive method, we used the effectiveness of the most likely alternative contraceptive she would use. We measured this with the question, “If you had to change to a new birth control method in the next year, which of the following methods would you consider using?” Participants selected each method they would consider and then ranked the selected methods from most to least likely method. Our “effectiveness of most likely contraceptive method” outcome was the difference between a woman’s score at baseline and follow-up.

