pregnant or avoid pregnancy?”³ We measured past pregnancy scares by asking: “Have you ever had a pregnancy scare; that is, thought you were pregnant when you didn’t want to be, but later discovered that you weren’t pregnant after all?” We measured numeracy using the Berlin single item numeracy scale.⁴ This scale has been tested and validated to show that people who answer this question correctly are in the top 50% of the population in numeracy.⁴ Data were also collected on the sexes of the woman’s past sex partners, whether she had ever seen the poster before, and whether there were any types of birth control the woman could not use for health/safety or cost reasons. The following variables were measured using questions from the National Survey of Family Growth (NSFG): biological sex, age, whether the participant was trying to conceive or was currently pregnant, sexual intercourse in the past three months, education, time since first sex, and marital status. Finally, the following variables were measured using questions from the National Longitudinal Survey of Adolescent to Adult Health (Add Health): race/ethnicity (Wave V), income (Wave IV), relationship status (Wave IV), and health insurance type (Wave IV).

Analysis

We first tested whether the demographic and other factors were balanced between our randomized groups using two-sample t-tests and likelihood-ratio tests as appropriate. We did not find any statistically significant imbalances for any of the variables. We conducted two-sample t-tests on the change in the mean score for each of our outcomes to test whether each poster improved the three primary outcomes relative to baseline and in comparison to the other poster. We used the Bonferroni correction to account for multiple comparisons. Using the

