same methods, we also tested the hypothesis that the three pre-specified subgroups (low numeracy, pregnancy scares, and no birth control) had greater increases in their mean scores for the patient-centered poster versus the CDC poster. We chose these subgroups because the patient-centered poster was designed to appeal to the needs of these groups. Finally, because correct answers to some of the questions on the Contraceptive Knowledge Assessment were not given by either poster, we could determine the proportion of the change in contraceptive knowledge that was attributable to the posters. We did this by analyzing the change in contraceptive knowledge separately for questions that did and did not have the correct answer provided by either poster. All analyses were conducted in Stata (Stata/SE 15, College Station, TX, US).

For our power calculations, we assumed an alpha of 1% and a power of 80%. For our final analysis sample of N=936, comparing the two posters we can detect a 3 percentage point difference in mean change in contraceptive knowledge (standard deviation of 0.18¹), a 0.8 percentage point difference in accuracy of perceived pregnancy risk (standard deviation of 0.05), and a 6 percentage point difference in the mean change in effectiveness of most likely contraceptive method (standard deviation of 0.35⁵).

References

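### With no unexposed arm, change from baseline cannot be credited to a poster for two of the three primary outcomes, and for knowledge only partly, through the item split

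*Combined protocol and SAP*

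**What the plan says.** The Study Design section describes the trial in one sentence: "We survey women before and after random administration of one of two educational posters informing readers about contraception". It adds: "Participants will then be randomly shown one of the two fact sheets". There are two arms, each with a poster, and no woman is re-asked without having seen one.

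The Measures section names three primary outcomes (contraceptive knowledge, effectiveness of the method most likely to be used, accuracy of perceived pregnancy risk) and states: "We gathered baseline and follow-up measures for each of these outcomes immediately before and after the intervention, respectively". The Procedures section puts everything in one sitting: "We expect that the survey will take 30 minutes, on average, to complete".

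The Analysis section sets two tasks for the t-tests on change scores: "to test whether each poster improved the three primary outcomes relative to baseline and in comparison to the other poster". For knowledge alone it adds a further step, "analyzing the change in contraceptive knowledge separately for questions that did and did not have the correct answer provided by either poster", in order to find how much of the change is due to the posters.

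**The concern.** Randomisation supports the comparison of one poster with the other. It does not support the comparison of each poster with baseline. In that second comparison the observed change is the sum of two parts: what the poster did, and what a second asking would have done anyway through familiarity, reconsideration or a guess at the answer the survey wants. A test of zero mean change rejects when the sum differs from zero, whichever part is responsible. Neither a larger sample nor a multiplicity correction separates the parts.

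At stake is a conclusion that each poster improved a primary outcome when the design does not identify that effect. The plan's own item split concedes that raw change in knowledge need not all come from the posters. No equivalent step exists for the other two outcomes.

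**Working it through.** **1. What could isolate retesting, outcome by outcome**

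- *Effectiveness of the intended method.* Measures asks the intention question at both time points and scores the difference. No item or group is free of poster exposure, so nothing isolates retesting.
- *Accuracy of perceived risk.* One question is asked twice and scored 0 or 1 against the method used in the past three months. That reference is effectively fixed within one sitting, so the score moves only if the answer moves. Nothing isolates retesting.
- *Knowledge.* Items that neither poster answers can serve as an internal control. The control is partial. Items are classed by whether either poster gives the answer, not by the poster the woman saw. No formal contrast of the two changes is stated. Equal retest gain in both item sets is implicitly assumed. The primary outcome in Measures remains the change in the full 25-item score.

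**2. The plan's own figures**

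The only power statement is for the poster-versus-poster comparison: N = 936, alpha 1%, power 80%, detectable differences of 3, 0.8 and 6 percentage points with SDs 0.18, 0.05 and 0.35. With 468 per arm (1:1 assumed, since the ratio is not stated) and two-sided alpha:

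detectable difference = (2.576 + 0.842) × SD × √(2/468) = 4.02, 1.12 and 7.82 points.

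The stated figures are therefore not reproduced for that comparison. This is a separate matter. Here I borrow only the SDs, N and alpha, as illustrative inputs.

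**3. Illustration for knowledge**

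Suppose there is no poster effect and a pure retest gain *g*, with SD 0.18 taken as the SD of change and two-sided alpha 1%. The plan says two-sample t-tests. For a comparison with baseline this could mean a one-sample (paired) test of the change, or literally follow-up against baseline as two samples, so both are shown.

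- Paired: SE = 0.18/√468 = 0.00832. Threshold = 2.576 × 0.00832 = 0.0214, and 0.0214 × 25 = 0.54 items.
- Literal two-sample: SE = 0.18 × √(2/468) = 0.01177. Threshold = 2.576 × 0.01177 = 0.0303, or 0.76 items.
- Probability of declaring improvement = Φ(g/SE − 2.576).

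| Retest gain | Paired | Two-sample |
|---|---|---|
| 0.25 item (0.01) | 8% | 4% |
| 0.5 item (0.02) | 43% | 19% |
| 0.75 item (0.03) | 85% | 49% |
| 1 item (0.04) | 99% | 79% |

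The Bonferroni level for these tests is not stated. If it were 5%/9 (three outcomes, each with two within-poster tests and one between-poster test), the critical value would be 2.773 and the thresholds 0.58 and 0.82 items.

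**4. Illustration for the other two outcomes (paired test)**

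- *Effectiveness.* If SD 0.35 is in points on the 0–3 scale, SE = 0.35/√468 = 0.0162 and the threshold is 0.042 points. A retest shift of 0.04 or 0.06 is declared an improvement in 46% or 87% of trials. If 0.35 is instead a proportion of the range, the threshold is three times as large, 0.125 points.
- *Accuracy.* With the plan's SD of 0.05, the threshold is 2.576 × 0.05/√468 = 0.006, or 0.6 percentage points. A change score of −1, 0 or 1 has SD of about √c when a share c of women change, so SD 0.05 corresponds to c = 0.0025, about 1 woman in 468. For assumed c of 5%, 10% and 20%, the SDs are 0.224, 0.316 and 0.447 and the thresholds 2.7, 3.8 and 5.3 points. A net shift of 4 points is then declared an improvement in 90%, 56% and 26% of trials.

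**5. The between-poster comparison**

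A retest shift that does not depend on the poster seen has the same mean in both arms and cancels in the difference. That test keeps its nominal level.

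**The case against.** Four objections deserve an answer.

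*The plan anticipated the problem.* A reader might infer that none of the three baseline comparisons can be interpreted, or that the plan overlooks retesting altogether. The documents do not support this. The item split is an internal control for knowledge, where practice effects are the most natural worry. This objection stands, and limits the full force of the point to the other two outcomes.

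*The within-poster test is not called a primary question.* This is also true. The plan labels outcomes, not comparisons, as primary, and powers only the poster comparison. How the results will be headlined cannot be known from the plan. But the test is stated, on all three primary outcomes, in terms of whether each poster improved them.

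*No retest gain is documented, and its direction is uncertain.* This stands too. A woman who intends to keep her method is scored on past use, so her score moves only if that intention flips. The risk item has a fixed reference, and no feedback on answers is described. Undirected changes of answer need not look like improvement, and a downward drift would hide a poster effect. The figures above show how small a shift would suffice, not that one occurred. The test still cannot attribute the change, whichever way any drift runs.

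*Deleting the test would be a post-hoc change.* The Analysis section already reports the outcome of the baseline balance checks. Dropping tests from the Bonferroni list at that stage would loosen the correction. This is accepted, and the fix avoids it.

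**Conclusion.** The concern holds in limited form. For effectiveness of the intended method and accuracy of perceived risk, the within-poster test cannot separate a poster effect from re-asking or demand effects, and nothing else in the plan does so. For knowledge, the item split does so partly.

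That conclusion rests on the design alone. Its size is only illustrative: for knowledge, retest gains of 0.25 to 1 item would give a declared improvement in 8% to 99% of trials (paired) or 4% to 79% (two-sample). These figures assume 468 women per arm, SD 0.18 as the SD of change, and two-sided alpha 1%, which the plan states for its power calculation without giving sidedness.

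A reader might go further and infer that the posters have no effect, or that the randomised comparison is compromised. Neither follows: the within-poster change is unattributed rather than shown to be spurious, and a retest shift common to both arms cancels between them.

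**What to change.** - Report within-poster change on each outcome as before-after change with a confidence interval, and state that it includes any effect of re-asking.
- Base conclusions about poster efficacy on the randomised between-poster difference.
- For knowledge, support any statement that a poster improved scores with a formal within-woman contrast: her mean change on items answered by the poster she saw, minus her mean change on items answered by neither poster. State the assumption that retest gain per item is the same in both sets, and label the contrast as an added supporting analysis.
- Keep the existing Bonferroni family unchanged.

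The cost is wording, a map of which items each poster answers, and one extra analysis of data already collected. The sponsor gives up an uncontrolled claim that each poster works on its own for two outcomes. Recovering that claim would take an unexposed, re-asked group, which these data do not contain.

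### Holm's step-down procedure would give the same familywise error control as the planned Bonferroni correction and never reject less; Bonferroni is valid, so this is a free efficiency gain of modest, scenario-dependent size

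*Combined protocol and SAP*

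**What the plan says.** The Measures section sets out the endpoints: "This study measured change in the mean scores for three primary outcomes" (contraceptive knowledge, effectiveness of the most likely method, and accuracy of perceived pregnancy risk). The Analysis section applies t-tests to the change scores "to test whether each poster improved the three primary outcomes relative to baseline and in comparison to the other poster". That is up to nine tests: three outcomes, each with two within-poster comparisons and one between-poster comparison. On multiplicity, the only sentence is "We used the Bonferroni correction to account for multiple comparisons". The same methods are then carried to subgroups: "we also tested the hypothesis that the three pre-specified subgroups (low numeracy, pregnancy scares, and no birth control) had greater increases". That could add nine more tests (three subgroups by three outcomes).

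The document does not give the number of comparisons in the correction, the familywise alpha, the sidedness, or whether within-poster and subgroup tests share a family with the between-poster tests. The power paragraph uses a per-test alpha of 1% and does not link it to a Bonferroni divisor. No reason is given for the single-step form.

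**The concern.** Bonferroni holds every test to alpha/m, even after other hypotheses in the family have been rejected. Holm orders the p-values from smallest to largest and compares them in turn with alpha/m, alpha/(m-1), and so on up to alpha, stopping at the first failure. It needs no assumption about dependence, and its first threshold is Bonferroni's. It therefore rejects whatever Bonferroni rejects and sometimes more, at the same familywise level. This is true however the family is defined.

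At stake is a real difference between posters whose p-value lies between alpha/m and the larger Holm threshold. Bonferroni would report it as non-significant, and the strictness would buy no better familywise guarantee.

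**Working it through.** **Inputs from the document (Analysis, power paragraph).** N=936; alpha 1%; power 80%; differences and SDs of 0.03/0.18 (knowledge), 0.008/0.05 (risk accuracy) and 0.06/0.35 (method effectiveness).

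**Assumptions, not in the document.** Familywise alpha 5%, two-sided tests, 1:1 allocation (468 per arm), and normal test statistics with a common correlation of 0 to 0.6.

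**1. The plan's own figure.** Detectable difference = SD × √(2/468) × (z for alpha + z for power), with √(2/468) = 0.0654. At two-sided 1%, the multiplier is 2.576 + 0.842 = 3.418. This gives 4.0, 1.1 and 7.8 points, not the stated 3, 0.8 and 6. Power at the stated differences is 49%, 45% and 52%. The stated values would follow if the SD of change were about 0.71 of the quoted SD, but the document does not say so. That is a separate matter. It is relevant here because it fixes the starting power in step 4.

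**2. Thresholds for m=3.**

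| Ordered p-value | Bonferroni | Holm |
|---|---|---|
| smallest | 0.0167 | 0.0167 |
| middle | 0.0167 | 0.025 |
| largest | 0.0167 | 0.05 |

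The smallest p-value faces the same threshold under both, so the chance of at least one rejection is identical.

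**3. Generic case, m=3, 80% power under Bonferroni.** The noncentrality is 2.394 + 0.842 = 3.236. Power at 0.0167, 0.025 and 0.05 is Φ(3.236 − 2.394) = 0.80, Φ(3.236 − 2.241) = 0.84 and Φ(3.236 − 1.960) = 0.90. These are the levels a test faces at Holm's first, second and third steps. Simulation (300,000 draws, correlation 0) gives the overall power for each truly different outcome:

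| Outcomes that truly differ | Bonferroni | Holm |
|---|---|---|
| one | 80% | 80% |
| two | 80% | 83% |
| three | 80% | 88% (87% at correlation 0.3) |

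Under the global null, the chance of any rejection is 4.9% for both. No draw had a Bonferroni rejection that Holm missed.

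**4. The plan's own differences and SDs, m=3.** Noncentrality = (difference/SD)/0.0654, which is 2.55, 2.45 and 2.62. At correlation 0.3:

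| Outcome | Bonferroni | Holm |
|---|---|---|
| Knowledge | 56% | 64% |
| Risk accuracy | 52% | 61% |
| Method effectiveness | 59% | 66% |

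At least one rejection: 85% for both. These figures take all three differences as real. If each outcome instead had the claimed 80% power at 1%, the change would be from 85% to 91%.

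**5. Within-poster tests in the family (m=9).** For 80% power at 0.05/9, the noncentrality is 2.773 + 0.842 = 3.61. With all three between-poster differences real and strong within-poster effects given an assumed noncentrality of 6 (correlation 0):

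| Within-poster effects | Bonferroni | Holm |
|---|---|---|
| all six null | 80% | 82% |
| two knowledge tests strong, four null | 80% | 85% |
| all six strong | 80% | 94% |

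With the plan's own differences at m=9 and correlation 0.3, power goes from 41/37/44% to 43/39/45% if all six are null, and to 64/61/66% if all six are strong. A common correlation simplifies how within- and between-poster statistics relate, so these rows show scale only.

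**6. Cost in error.** With one or two true nulls among the three tests (plan's differences, correlation 0.3), Holm's familywise error is higher than Bonferroni's: 1.7% to 3.3% with one null and 3.3% to 4.2% with two. It stays below 5%.

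**The case against.** The strongest reply is that nothing is broken. Bonferroni is conventional, valid under any dependence, and gives simultaneous intervals that agree with its decisions. That stands, and it is why this is an efficiency point.

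The size can also be oversold, and these objections stand too:

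- The 8-point gain needs real differences on all three outcomes, which nothing in the document establishes. With one real difference the gain is essentially nil.
- The rise to 94% needs six strong within-poster effects. A strong gain after reading a poster is most natural to expect for knowledge, which accounts for only two of the six.
- Power to detect all three differences rises more (51% to 72% in the generic case at correlation 0), but the document does not make winning on all three a success criterion.
- Holm cannot be applied until the family is defined, and the document leaves that open.
- The Analysis section is partly in the past tense and reports a completed balance check. Changing now to a rule that can only add rejections is a post hoc change unless disclosed.

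None of this touches the core comparison: for any family, Holm keeps the error guarantee and never rejects less.

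**Conclusion.** The point holds as a free improvement. Single-step Bonferroni gives away power on tests other than the one with the smallest p-value. At m=3 the gain is about 0, 3 or 8 points per truly different outcome in the generic case, and about 7 to 9 points on the plan's own inputs if all three differences are real. At m=9, for outcomes with 80% power under Bonferroni, it runs from about 2 to about 14 points. All of these rest on an assumed 5% two-sided familywise level, 1:1 allocation and an assumed family.

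A reader might infer three stronger things that the document does not support:

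- **That the planned correction is wrong or inflates error.** It does neither.
- **That two particular outcomes, such as risk accuracy and intended method, are the losers.** The plan does not rank its outcomes, and Holm orders p-values, so which test benefits depends on the data.
- **That the trial is more likely to find something.** The chance of at least one rejection is the same under both procedures.

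**What to change.** In the Analysis section, first name the family of tests and the familywise alpha, including whether the within-poster and subgroup tests belong to it. Then replace Bonferroni with the Holm step-down procedure on that same family and report Holm-adjusted p-values. Keep Bonferroni-level confidence intervals where simultaneous intervals are wanted, and note that an interval may include zero when Holm rejects. Because the analysis is described as already done, label the switch as a change from the stated method and show the Bonferroni result beside it.

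The cost is a sentence or two of text and a few lines of code working from the unadjusted p-values, with no new data and no loss of the familywise guarantee. The trade-offs are that simple simultaneous intervals do not narrow and that the change must be disclosed.

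### Bonferroni is applied without a stated family, level or threshold, the 1% power alpha is tied to no set of tests, and the stated detectable differences do not follow even at that 1%

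*Combined protocol and SAP*

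**What the plan says.** The Measures section names three primary outcomes: "This study measured change in the mean scores for three primary outcomes". They are contraceptive knowledge, effectiveness of the most likely method, and accuracy of perceived pregnancy risk.

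The Analysis section uses t-tests on the change scores "to test whether each poster improved the three primary outcomes relative to baseline and in comparison to the other poster". Its only statement on multiplicity follows directly: "We used the Bonferroni correction to account for multiple comparisons". It then extends the testing to subgroups, "same methods, we also tested the hypothesis that the three pre-specified subgroups (low numeracy, pregnancy scares, and no birth control", and to two sets of knowledge items, by "analyzing the change in contraceptive knowledge separately for questions that did and did not have the correct answer provided by either poster".

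The power paragraph that closes the section says "we assumed an alpha of 1% and a power of 80" per cent. It continues "For our final analysis sample of N=936, comparing the two posters" and gives three detectable differences: 3 points for knowledge (SD 0.18), "a 0.8 percentage point difference in accuracy of perceived pregnancy risk (standard deviation of 0.05"), and 6 points for method effectiveness (SD 0.35).

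The plan does not state how many tests share the correction, the familywise level, the resulting threshold, whether the 1% is one- or two-sided, or where the 1% comes from.

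**The concern.** A Bonferroni threshold is a familywise level divided by a number of tests. With neither given, a reader cannot tell which p-values count as significant. At an assumed 5% level, a between-poster p-value between 0.0056 and 0.0167 is significant if the family is the three between-poster tests, and not if it is all nine primary tests.

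The power paragraph should show what the trial can detect at the threshold it will use. Because its 1% is not tied to a family, that link is missing. The detectable differences must also follow from the alpha, power, sample size and standard deviations printed beside them. If they do not, readers will overrate the trial's sensitivity and may read a null result as stronger evidence of no difference than it is.

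**Working it through.** **Inputs from the documents.** Total N = 936, alpha 1%, power 80%, SDs 0.18 / 0.05 / 0.35, stated differences 0.03 / 0.008 / 0.06. The SDs are taken as given and treated as SDs of the change score.

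**Assumptions.** Equal allocation, so 468 per arm; two-sided tests; 5% familywise level, varied below.

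**Counting the tests.**
- Between posters: 3 outcomes × 1 = 3.
- Within posters: 3 outcomes × 2 = 6, so 9 primary tests in all.
- Subgroups: 3 × 3 = up to 9 more, 18 in all.
- Knowledge item sets: at least 2 more.

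At 5%, the thresholds are 0.05/3 = 0.0167, 0.05/9 = 0.0056 and 0.05/18 = 0.0028. Exactly 1% needs five tests.

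**Attempt to reproduce the plan's figures.** Normal approximation: MDD = SD × (z(1−α/2) + z(0.80)) × √(2/468), with √(2/468) = 0.06537 and z(0.80) = 0.8416. At α = 0.01, z = 2.5758, so the multiplier is 3.4175 × 0.06537 = 0.2234.
- Knowledge: 0.18 × 0.2234 = 4.02 points (stated 3).
- Risk accuracy: 0.05 × 0.2234 = 1.12 points (stated 0.8).
- Effectiveness: 0.35 × 0.2234 = 7.82 points (stated 6).

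The recomputed values exceed the stated ones by 34%, 40% and 30%. In reverse, power = Φ(d/(SD × 0.06537) − 2.5758). For knowledge, 0.03/(0.18 × 0.06537) = 2.550, so power is Φ(−0.026) = 49%. The other two give 45% and 52%. For 80% power at the stated differences, total N would have to be 1682 / 1826 / 1590.

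Rounding does not explain this. Differences of 3.49, 0.85 and 6.49 points, about the largest that round to the stated values, have power of 65%, 51% and 60%. A one-sided 1% gives 3.73 / 1.04 / 7.25. The stated values do appear, after rounding, in two ways: with one-sided 5% (2.93 / 0.81 / 5.69), or with 1% and 936 in each arm instead of in total (2.84 / 0.79 / 5.53). The documents do not say whether either was used.

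**Effect of the family.** Same formula, points for knowledge / accuracy / effectiveness:

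| Threshold | Basis | Multiplier | MDD | Change from 1% | Power at stated differences |
|---|---|---|---|---|---|
| 0.0167 | 5%/3 | 0.2115 | 3.8 / 1.06 / 7.4 | −5% | 56 / 52 / 59% |
| 0.0100 | stated | 0.2234 | 4.0 / 1.12 / 7.8 | none | 49 / 45 / 52% |
| 0.0056 | 5%/9 | 0.2363 | 4.3 / 1.18 / 8.3 | +6% | 41 / 37 / 44% |

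A difference with 80% power at 1% has 85% at 0.0167 and 74% at 0.0056.

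**Sensitivity to the 5% assumption.**
- 10% familywise level over three tests (threshold 0.0333): z = 2.128, multiplier (2.128 + 0.8416) × 0.06537 = 0.1941, giving 3.5 / 0.97 / 6.8.
- 2.5% over nine tests (0.0028): multiplier 0.2506, giving 4.5 / 1.25 / 8.8.

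Every case exceeds 3 / 0.8 / 6.

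**The case against.** The strongest reply is that the shortfall has little to do with multiplicity. This stands. The stated differences already fail at the plan's own 1%, and replacing 1% with 0.0167 would slightly improve the detectable differences. A reader might infer that the undefined family explains why the trial cannot detect 3 / 0.8 / 6 points; the table shows that it explains only a small part.

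A reader might also infer that the 1% is wrong because no grouping of the tests gives five. The documents do not support that. Three between-poster tests plus two item-set analyses make five, and 0.05/6 = 0.0083 or 0.10/9 = 0.011 could be loosely rounded to 1%. The plan confirms none of these, so the defensible statement is that the 1% is not linked to any family.

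An 18-test family is a possible but weaker reading. The Bonferroni sentence directly follows the primary tests, and the subgroups come later under the same methods, which may mean a separate application. At 0.0028 the figures would rise by 12% over the 1% values.

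Finally, Bonferroni is valid, and within-poster change and the subgroups are questions the sponsor chose to ask. Nothing in the documents requires them to be made descriptive. That is a trade-off for the sponsor, and Holm is an improvement in power, not the correction of an invalid method.

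**Conclusion.** The point holds in two parts. First, the multiplicity rule is incomplete: the family, its level and the threshold are not stated, and the 1% used for power is not connected to them. Second, the stated detectable differences are too small. At the stated two-sided 1% the recomputed values are 30% to 40% larger, and power at the stated differences is 45% to 52%, not 80%. The second part is the larger one; under an assumed 5% familywise level, the choice between three and nine tests moves the figures by about −5% to +6%.

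The conclusion rests on 1:1 allocation, the stated SDs, and two-sided testing; one-sided 1% narrows the gap but does not close it. The second part does not depend on the assumed familywise level, because the figures fail at the alpha the plan itself gives.

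The analysis text is in the past tense and already reports the balance tests, so the outcome results may have been known when it was written. A reader might infer that the family was chosen to suit them. The documents give no evidence of that; they only leave it impossible to check.

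**What to change.** - State which tests form the family, the familywise level and its sidedness. Whether the within-poster and subgroup tests are inside it is the sponsor's choice, but it must be written down.
- Use Holm instead of plain Bonferroni within that family. At 5%, three tests would be judged in order of p-value at 0.0167, 0.025 and 0.05; nine would start at 0.0056. Familywise control is the same and power is never lower. The small cost is that simultaneous confidence intervals are less simple than with Bonferroni.
- Restate the detectable differences at the first-step threshold actually used, with the per-arm sample size and sidedness shown. For three or nine tests at 5% they are the 0.0167 and 0.0056 rows of the table.
- If results are already known, say that the family was fixed afterwards and show unadjusted p-values beside the adjusted conclusions. This matters most if the three-test family is chosen, since it gives the more lenient of the two thresholds.

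The cost is a few sentences and a recalculation, with no new data. The restated sensitivity will look clearly less favourable: for knowledge, about 3.8 to 4.3 points in place of 3.
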